Data Analysis for Drug Repurposing for Effective Alzheimer's Medicines – Pentoxifylline vs Cilostazol

NCT05635370

July 7, 2023

1. Comparison Details

a. Intended aim(s)

To evaluate the comparative risk of dementia onset between patients treated with Pentoxifylline versus cilostazol for peripheral artery disease (PAD).

b. Primary endpoint

Incident dementia (i.e., Alzheimer's disease, vascular dementia, senile, presenile, or unspecified dementia, or dementia in other diseases classified elsewhere).

2. Person responsible for implementation

[name]

3. Data Source(s)

Medicare, 2008-2018

4. Study Design Diagrams

[figure not shown]
[figure not shown]

Figure- Alternate analysis approaches

[figure not shown]
■■■ Included person-time
 ■■■ Excluded person-time

Provides 'on treatment' estimates for the outcome risk and addresses exposure person-time misclassification

Analysis 1

[figure not shown]

Analysis 3

[figure not shown]

Addresses reverse causation due to preferential treatment initiation related to unrecorded cognitive impairment at study start and informative-censoring

Analysis 2

Analysis 4

5. Cohort Identification

a. Cohort Summary

This study will employ a new user, active comparator, observational cohort study design comparing Pentoxifylline versus Cilostazol. The patients will be required to have continuous enrollment during the baseline period of 365 days before initiation of study drugs (cohort entry/index date). Follow-up for the outcome (dementia) differs between analyses. Follow-up begins the day after drug initiation (analysis 1, 3, 4); 180 days after drug initiation (analysis 2).

b. Key details regarding cohort creation

Index date:

- Day of initiation of new Pentoxifylline versus Cilostazol use

Inclusion criteria for analyses 1, 3, 4:

- Aged \geq 65 years on the index date
- 365 days enrollment in Medicare Parts A, B, and D with no HMO coverage prior to index date
- No use of Pentoxifylline versus Cilostazol, any time prior to index date (all available lookback approach with a minimum of 365 days)
- No diagnosis of dementia any time prior to and including index date
- No history of nursing home admission recorded in any time prior to and including index date
- At least two claims with peripheral artery disease diagnosis recorded in 365 days prior to index date (ICD-9 or ICD-10 codes)¹

Inclusion criteria for analysis 2:

- Aged \geq 65 years on the index date

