- 365 days enrollment in Medicare Parts A, B, and D with no HMO coverage prior to index date
- No use of Pentoxifylline versus Cilostazol, any time prior to index date (all available lookback approach with a minimum of 365 days)
- No diagnosis of dementia any time prior to and including index date
- No history of nursing home admission recorded in any time prior to and including index date
- At least two claims with peripheral artery disease diagnosis recorded in 365 days prior to index date (ICD-9 or ICD-10 codes)¹

- 180-day continuous use of Pentoxifylline versus Cilostazol starting on the index date

c. Flowchart of the study cohort assembly

	Less Excluded Patients	Remaining Patients
All patients		23,466,175
Did not meet cohort entry criteria	-23,393,311	72,864
Excluded due to insufficient enrollment	-45,683	27,181
Excluded based on Dementia Exclusion	-6,100	21,081
Excluded based on Nursing Home Admission	-4,080	17,001
Excluded based on Peripheral artery disease Diagnosis	-4,524	12,477
Excluded anyone aged <65 at index	-2,079	10,398
Patients in Pentoxifylline group		1,701
Patients in Cilostazol group		8,697
Final cohort		10,398

6. Variables

a. Exposure-related variables:

Study drug:

The study exposure of interest is initiation of Pentoxifylline

Comparator:

Cilostazol

b. Covariates:

Demographics	
Age	Region
Gender	Calendar year of index date
Race	Low income subsidy

Dementia risk factors	
Diabetes	Depression
Obesity	Anxiety
Hypertension	Bipolar disorder
Coronary artery disease	Schizophrenia

Markers for healthy behavior, frailty, healthcare use	
Smoking	Number of hospitalizations
Mammography	Number of physician office visits
Colonoscopy	Number of serum creatinine tests ordered
Fecal occult blood test	Composite frailty score
Influenza vaccination	Number of C-reactive protein tests ordered
Pneumococcal vaccination	Osteoporosis
Herpes zoster vaccination	Fractures
Bone mineral density test	Falls
Number of distinct generic agents	Use of supplemental oxygen
Number of emergency room visits	Combined comorbidity score
Number of outpatient visits	

Comedication use	
Lithium	Diuretics
Anti-epileptic mood stabilizers	Nitrates
Anti-epileptics (other than mood stabilizers)	Lipid lowering drugs

Atypical antipsychotics	Non-insulin diabetes medications
Benzodiazepines	Insulin
Serotonin-norepinephrine reuptake Inhibitors	Antidepressants
Selective serotonin reuptake inhibitors	Angiotensin II receptor blockers (ARBs)

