Tricyclic antidepressants (TCAs)	Angiotensin converting enzyme inhibitors (ACEi)
Typical antipsychotics	Calcium channel blockers
Anticoagulants	Beta blockers
Antiplatelet agents	

Comorbid conditions	
Atrial fibrillation	Chronic liver disease
Coronary artery disease	Asthma
Heart failure	Ischemic heart disease
Stroke or transient ischemic attack	Chronic obstructive pulmonary disease
Peripheral vascular disease	Malignancy
Hyperlipidemia	Drug or alcohol abuse or dependence
Renal dysfunction	Venous thromboembolism
Rheumatoid Arthritis	Hypertension

Other PAD treatments and PAD severity indicators	
Critical limb ischemia Thrombolytic therapy (streptokinase, urokinase, alteplase, tissue plasminogen activator (tPA), pro-urokinase, reteplase, tenecteplase and Staphylokinase)	Number of cardiologist visits Number of hospitalizations with PAD

ICD-9, ICD-10, HCPCS, and NDC codes used to define the covariates listed above are available in Appendix A.

c. Outcome variables and study follow-up:

- **Primary outcome:** incident dementia, i.e., Alzheimer's disease, vascular dementia, senile, presenile, or unspecified dementia, or dementia in other diseases classified elsewhere. Outcome will be defined by 1 inpatient

claim or 2 outpatient claims in analysis 1, 2, 3. In analysis 4, the outcome will be defined by 1 inpatient or 1 outpatient claims and 1 prescription claim for a symptomatic treatment [donepezil, galantamine, rivastigmine, and memantine] within 6 months of each other with outcome date assigned to second event in the sequence.

- Secondary outcomes: Individual component:

Alzheimer's disease

Condition	ICD-9 and ICD-10 codes
Alzheimer's disease	331.0*, F00*, G30*
Vascular dementia	290.4*, F01*
Senile, presenile, or unspecified dementia	290.0*, 290.1*. 290.3*, 797*, F03*
Dementia in other diseases classified elsewhere	331.1*, 331.2*, 331.7*, 294.1*, F02*

For analysis 1,3, and 4 the follow-up will start the day after initiation of Pentoxifylline and Cilostazol and will continue until the earliest date of the following events:

- The first occurrence of the outcome of interest
- The date of end of continuous registration in the database,
- End of the study period,
- Measured death event occurs,
- The date of drug discontinuation, defined as the date of the last continuous treatment episode of the index drug (Pentoxifylline and Cilostazol) plus a defined grace period (i.e., 90 days after the end of the last prescription's days' supply in main analyses).

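### Patients already dispensed a dementia drug before the index date are not excluded, so some can later count as incident dementia

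*Combined protocol and SAP*

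**What the plan says.** Section 5b has two inclusion lists, one for analyses 1, 3 and 4 and one for analysis 2. Both contain the same dementia criterion: "No diagnosis of dementia any time prior to and including index date". Both add a second safeguard: "No history of nursing home admission recorded in any time prior to and including index date". The only prior-drug exclusion in either list concerns pentoxifylline and cilostazol. Both lists require at least 365 days of Part D enrollment before index.

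The flowchart in Section 5c has one step labelled "Excluded based on Dementia Exclusion", with no definition, followed by "Excluded based on Nursing Home Admission". It has no separate step for dementia drugs.

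Section 6c defines the outcome in analyses 1-3 by one inpatient or two outpatient claims. Analysis 4 combines one diagnosis claim with "1 prescription claim for a symptomatic treatment [donepezil, galantamine, rivastigmine, and memantine", the two falling "within 6 months of each other with outcome date assigned to second event in the sequence". This is the only place where the four drugs are named. They are absent from the covariates in Section 6b and from the balance table in Section 8.

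The figure text in Section 4 names "unrecorded cognitive impairment at study start" as a source of bias that the alternate analyses are meant to address.

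**The concern.** The stated aim is the onset of dementia after drug initiation, so patients who already have it at index should not be at risk. After index, the plan accepts a fill of one of these four drugs as half of a dementia definition. Before index, it ignores the same fill, although the required Part D data would show it. A prior fill does not prove dementia, because some patients may use these drugs for other reasons. It is still a direct signal of possible unrecorded impairment, which the plan itself names as a concern.

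If such patients are admitted and coded later, the event count mixes onset with late recording of existing disease. Equal numbers in the two arms would pull the hazard ratio toward 1. Unequal numbers could move it in either direction.

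**Working it through.** **1. How a prior user becomes an incident case**

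| Step | Rule in the plan | Patient treated before index, no dementia code |
|---|---|---|
| Entry (5b) | No earlier diagnosis, no nursing-home history | Admitted if neither is recorded |
| Matching (6b, 8) | Four drugs not among the covariates | Prior use neither matched on nor shown |
| Outcome, analyses 1-3 (6c) | 1 inpatient or 2 outpatient claims | Counted once coded in follow-up |
| Outcome, analysis 4 (6c) | 1 diagnosis claim plus 1 fill within 6 months | One later diagnosis claim can suffice |

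In analysis 4 the text does not require the fill to come after index. A pre-index fill can pair only with a diagnosis claim in about the first 6 months of follow-up. After that, a continuing user's refill supplies the second component.

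**2. What the existing protections do**

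- Any single prior diagnosis excludes, with no claim-count threshold. This cannot catch a patient who has no code.
- The flowchart figures reproduce: 27,181 − 6,100 = 21,081 and 21,081 − 4,080 = 17,001. The dementia step removes 6,100/27,181 = 22.4%, and the nursing-home step a further 4,080/21,081 = 19.4%. Few treated but uncoded patients may therefore remain. Both steps precede the PAD and age exclusions, so these percentages do not describe the final cohort.
- After matching, standardized differences are 0.02 for the frailty score and 0.00 for number of distinct prescriptions (0.21 and 0.23 before matching). These are general measures that do not identify the four drugs.
- Analysis 2 starts follow-up at day 180. Patients first coded after that, within its 1,095-day maximum, still count.

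**3. How few patients would make up 10% of events**

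Inputs from Section 8: 1,687 matched patients per arm, so n = 2 × 1,687 = 3,374. Assumed, because the documents give neither: incidence r = 0.015 to 0.040 per person-year, and mean follow-up T = 0.5 to 2 years. The 10% share is a chosen benchmark.

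True incident events number about n × r × T. For k prior users coded in follow-up to form 10% of all events, k / (k + nrT) = 0.1, so k = nrT × 0.1/0.9.

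| T (years) | r = 0.015: nrT | k (% of n) | r = 0.040: nrT | k (% of n) |
|---|---|---|---|---|
| 0.5 | 25.3 | 2.8 (0.08%) | 67.5 | 7.5 (0.22%) |
| 1 | 50.6 | 5.6 (0.17%) | 135.0 | 15.0 (0.44%) |
| 2 | 101.2 | 11.2 (0.33%) | 269.9 | 30.0 (0.89%) |

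This is a threshold and not an estimate of how many such patients there are. It counts every coded prior user as prevalent dementia, so fewer true prevalent cases would have less effect. It does not apply to analysis 2. The flowchart has no 180-day continuous-use step, so that sample size is not given.

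**The case against.** The strongest reply is that a possibility has been shown, but not a bias of known size. The threshold rests on assumed incidence and follow-up and on an arbitrary 10% share. Even at 10%, the effect can be small. With equal numbers per arm and a true ratio of 0.80, the true events are 0.40 and 0.50 of the total. Adding 0.05 to each gives 0.45/0.55 = 0.82. The shift in the log ratio is about 0.02. With 25-270 events, the standard error of the log hazard ratio is roughly 2/√events, or 0.40 to 0.12. A larger effect needs imbalance: a 1:2 split of the same 10% moves a null ratio to (0.45 + 0.033)/(0.45 + 0.067) = 0.94, and the documents give no evidence of imbalance. This all stands as a limit on importance. It does not show that prior use is balanced, because no row of the balance table measures it, and imprecision does not excuse an avoidable bias.

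The second reply is that a drug criterion may already be in place. The diagrams under "Figure- Alternate analysis approaches" are not shown in the text reviewed, and the flowchart's dementia step is undefined. That lowers certainty. The only written criterion nevertheless refers to diagnosis.

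Third, because Section 6c calls the outcome incident and starts follow-up after initiation, it is natural to read the analysis 4 pair as falling within follow-up. That is a fair reading, and a sentence would settle it. It would not deal with continuing users, whose refills also fall within follow-up.

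Finally, excluding prior users also removes some patients without dementia. That is a real, probably small, cost.

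**Conclusion.** The concern holds. As written, both inclusion lists admit patients dispensed one of the four drugs before index, and those first coded afterwards can meet the incident dementia definition in every analysis. The plan's safeguards reduce the number but cannot identify these patients. The number affected, the direction of any bias and the shift in the hazard ratio cannot be determined from the documents, and none is claimed. Under the stated assumptions, well under 1% of the matched sample would be enough to supply a tenth of the events.

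The change is worth making because the data are already required and the question can be settled by a count. Confidence is medium, because a drug criterion may exist in material that was not available.

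**What to change.** - Add to both inclusion lists in Section 5b a criterion that the patient has had no dispensing of donepezil, galantamine, rivastigmine or memantine at any time up to and including the index date.
- Show the number removed by arm in the flowchart, and re-run the matching and the balance table.
- In Section 6c, require both components of the analysis 4 outcome to occur after follow-up starts. This does not replace the exclusion, because a continuing user's refill would supply the prescription component.
- For analysis 2, if the drug exclusion is carried forward to day 180, carry the diagnosis exclusion to day 180 as well.
- An analysis without the new exclusion can be kept as a sensitivity analysis.

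If the sponsor prefers not to change the main cohort, the minimum is to report prior use by arm and run the exclusion as a sensitivity analysis. If the flowchart's dementia step already covers these drugs, it is enough on the exclusion to state that in both lists.

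The cost is one more Part D exclusion, in a plan that already uses NDC codes to define covariates, plus re-running the matching. The loss of patients is probably small, and some of those lost may have used the drugs for other reasons.

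### Recorded cognitive impairment short of dementia, and Parkinson's disease, are neither excluded nor in the propensity score, so balance on recorded baseline cognitive status is neither sought nor checked

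*Combined protocol and SAP*

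**What the plan says.** Section 5b gives two inclusion lists, one for analyses 1, 3 and 4 and one for analysis 2. On cognitive or functional grounds both contain the same two conditions: "No diagnosis of dementia any time prior to and including index date" and "No history of nursing home admission recorded in any time prior to and including index date". The section gives no codes for the dementia exclusion.

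In section 6b, the block headed "Dementia risk factors" has eight entries: diabetes, obesity, hypertension, coronary artery disease, depression, anxiety, bipolar disorder and schizophrenia. Among the comorbid conditions the only neurological entry is "Stroke or transient ischemic attack". A "Composite frailty score" is listed without its components. The codes "used to define the covariates listed above are available in Appendix A".

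The figure text in section 4 names as a threat "reverse causation due to preferential treatment initiation related to unrecorded cognitive impairment at study start". Section 7 claims control of measured confounding only.

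**The concern.** The plan accepts that cognitive impairment at study start can distort the comparison, but its text speaks only of impairment that was not recorded. Impairment that was recorded is the part claims data can deal with directly, and the plan makes no provision for it.

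Take a patient with mild cognitive impairment coded three months before the index date and no dementia code. The patient is eligible, and nothing in the listed covariates separates that patient from a cognitively normal one when pairs are formed. If dementia is then coded by one inpatient or two outpatient claims (the rule for analyses 1 to 3), the patient counts as an incident case. A patient with Parkinson's disease can follow the same route, because dementia in other diseases classified elsewhere (F02*) is part of the outcome.

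If such patients were more common in one matched arm, the hazard ratio would move away from the truth in that direction. The balance table, as specified, would not show it.

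**Working it through.** **1. Where the conditions could appear.**

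| Place | Mild cognitive impairment | Memory or other cognitive symptoms | Parkinson's disease |
|---|---|---|---|
| 5b, both inclusion lists | no | no | no |
| 6b, all covariate blocks | no | no | no |
| Section 8, balance table | no | no | no |

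Appendix A is not in the available text, but it is described as coding the covariates already listed, so it would not be expected to add others. The 6b list is not perfectly complete: the balance table has a DMARD row that 6b lacks. The table has no row for these conditions either.

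**2. The plan's own figures.** The flowchart in 5c reproduces: 72,864 − 45,683 = 27,181; − 6,100 ("Excluded based on Dementia Exclusion") = 21,081; − 4,080 = 17,001; − 4,524 = 12,477; − 2,079 = 10,398 = 1,701 + 8,697. Standardized differences, computed as (p1 − p0)/√{[p1(1 − p1) + p0(1 − p0)]/2}, also reproduce. Critical limb ischemia is 0.29 crude (394/1,701 vs 1,058/8,697) and 0.00 matched (381/1,687 vs 380/1,687). None of these figures tells us how often the omitted conditions occur in either arm.

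**3. Which analyses are exposed.** Analyses 1, 3 and 4 start follow-up the day after initiation. Analysis 2 starts at 180 days and requires 180 days of continuous use, with follow-up up to 1,095 days. Its entry list still admits patients with recorded impairment, so conversion after day 180 counts.

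**4. Possible size.** For a binary factor left unbalanced, the approximate multiplier on the treatment hazard ratio is

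(1 + (R − 1)p1) / (1 + (R − 1)p0),

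where p1 and p0 are its prevalences in the matched pentoxifylline and cilostazol arms and R is its hazard ratio for dementia. All three inputs are assumptions.

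| p1 vs p0 | Ratio | R | Calculation | Multiplier |
|---|---|---|---|---|
| 1% vs 1% | 1:1 | 5 | 1.04/1.04 | 1.00 |
| 1.2% vs 1% | 1.2:1 | 5 | 1.048/1.04 | 1.008 |
| 1.8% vs 1.5% | 1.2:1 | 10 | 1.162/1.135 | 1.024 |
| 2% vs 1% | 2:1 | 5 | 1.08/1.04 | 1.038 |
| 3% vs 1.5% | 2:1 | 10 | 1.27/1.135 | 1.119 |
| 1% vs 2% | 1:2 | 5 | 1.04/1.08 | 0.963 |
| 1.5% vs 3% | 1:2 | 10 | 1.135/1.27 | 0.894 |

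With 1,687 patients per matched arm, 2% vs 1% is about 34 vs 17 patients, a standardized difference of about 0.08; 3% vs 1.5% is about 0.10.

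**5. Which ratio is nearer.** Crude ratios for the closest listed conditions are depression 14.1/11.8 = 1.19, falls 6.3/5.4 = 1.17, and stroke or TIA 14.2/13.5 = 1.05. These are before matching and lie much nearer 1.2:1 than 2:1.

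**The case against.** A reader might infer that the arms are in fact unbalanced on cognitive status, because pentoxifylline initiators look sicker before matching: frailty score 0.21, distinct prescriptions 0.23, comorbidity score 0.18, critical limb ischemia 0.29. The documents do not support that step. After matching, the same rows read 0.02, 0.00, −0.02 and 0.00. Falls, depression, antipsychotic use, stroke and outpatient visits are matched too, and prior nursing home residents are excluded. Only the part of cognitive status not carried by those variables could remain unbalanced. The frailty score may be a partial proxy; its components are not shown. Nor are the crude differences all one way: smoking (−0.19) and coronary artery disease (−0.16) are more common with cilostazol.

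Both drugs are started for peripheral artery disease, and nothing in the documents shows why a cognitive code would favour one of them. The outcome rule also slows conversion: one outpatient claim does not suffice in analyses 1 to 3, and analysis 4 needs a diagnosis claim and a symptomatic-drug claim within six months. The lag in analysis 2 works whether or not the impairment was coded.

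All of this stands, and it limits the likely size. It does not fill the gap. Matching on correlates is no check on the factor itself, and the lag covers one analysis of four. Rarity is no reason to omit the conditions, since the plan carries schizophrenia (2 and 8 patients) and lithium (2 and 14).

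**Conclusion.** The omission is confirmed by direct reading and applies to all four analyses, with partial relief in analysis 2. What can be said is that balance on recorded baseline cognitive status is neither sought nor checked. It cannot be said that the arms differ, that the hazard ratio is biased, or in which direction.

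The possible shift runs from nothing at equal prevalence, through about 1-2% at 1.2:1, to about 4-12% at 2:1, and it could go either way. A reader might take 4-12% as the expected bias. It is the result of assuming that one arm has twice the prevalence after matching, which no figure in the documents suggests. The range also rests on assumed prevalences of 1-3%, assumed hazard ratios of 5-10, and a formula that ignores depletion of high-risk patients over follow-up.

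Two limits remain. The codes behind the dementia exclusion are not given, so its exact scope cannot be verified, and Appendix A was not available. This is a modest gap that is cheap to close, in a study whose endpoint is dementia.

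**What to change.** - In section 6b, add three baseline covariates to "Dementia risk factors": mild cognitive impairment, memory-loss or other cognitive symptom codes, and Parkinson's disease. Give their codes in Appendix A.
- Include them in the propensity score, re-match, and show their crude and matched rows in the section 8 table.
- Repeat analysis 1 without patients who have a baseline cognitive-impairment code, as a sensitivity analysis.

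If the current match is kept, the least that would help is the standardized differences for these three conditions in the existing 1,687 pairs. Values near zero would largely settle the point; otherwise the re-match is needed.

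The cost is three covariates from claims already held, one re-match and a revised balance table. A few pairs may be lost; the documents do not allow the number to be computed. The present match loses 14 of 1,701 pentoxifylline patients (1,701 − 1,687).
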